8. GENERAL SPECIFICATIONS FOR STATISTICAL ANALYSES

This section provides a general overview of the methods to analyze the study data. Specific analyses will be reported in the appropriate section 9.

Continuous (quantitative) variables will be summarized using descriptive statistics including number of non-missing values, mean, standard deviation (SD), median, minimum, and maximum. Selected continuous variables will also be described in classes (e.g. age, QTc, etc.)

Frequency and percentage will be provided for categorical variables and generated for parameter estimates of interest. In general, the denominator for the percentage calculation will be based upon the number of treated patients, unless otherwise indicated, by dose level and overall in the study population.

For the efficacy analysis, the percentage of the ORR, according to the RECIST 1.1 [2] or mRECIST [8], will be reported both as a point estimate and by means of 95% CIs .

The survival curve and the quartiles (25th percentile, median, 75th percentile) will be estimated for the time-to-event endpoints (i.e. DoR, PFS and OS) using the Kaplan-Meier method [9] and will be reported along with the corresponding 95% Confidence Intervals (CIs). Reverse Kaplan-Meier method [10] will be used to estimate the median length of follow-up for PFS and OS.

8.1. Handling Missing Data

Specific information for imputing missing data, where appropriate, will be documented in the separate appendix TLGs Mock-ups and Algorithms. Except for time related endpoints, missing observations will not be imputed, unless otherwise noted.

8.2. Analysis Conventions

All collected data will be presented in listings. Data not subject to analyses according to this plan will not appear in any tables or graphics but will be included only in the data listings.

Partial dates in principle will not be imputed except for date of birth. Only year of birth will be collected in the database and to estimate patient's age, December 31st will be used to replace the missing month and day, respectively.

Censoring rules for time-to-event endpoints are reported in the appendix TLGs Mock-ups and Algorithms, provided as a separate document.

Study day will be calculated in reference to the date of first study treatment dose. For assessments conducted on or after the first dose, study day is calculated as (assessment date – first dose date +1). For assessments conducted before the first dose, study day is calculated as (assessment date – first dose date). The study day will be displayed in all relevant data listings.

The baseline visit will correspond to the last assessment with non-missing result performed before initial study drug administration, unless otherwise indicated in the appendix TLGs Mock-ups and Algorithms.

All analysis conventions are detailed in the separate appendix TLGs Mock-ups and Algorithms.

8.3. Analysis Software

Data processing, data listings, tabulation of descriptive statistics, calculation of inferential statistics and graphical representations will be performed using SAS® Software (release 9.4 or higher) for Windows, unless otherwise specified.

9. STATISTICAL ANALYSES

9.1. Patient Disposition

Patients' disposition and reasons for ending the treatment and the study will be presented in frequency distribution tables and individual data listings by study phase and dose level. The patients not meeting the eligibility criteria, and who are considered protocol violators will be identified and described by individual data listing by study phase. Reasons for stopping treatment will be summarized as frequency distribution in the treated patient population. Untreated patients will be identified and described separately.

9.2. Protocol Deviations

Protocol deviations will be classified as critical, major or minor based on MPSA-153-001 Protocol Deviations classification document. The patients not meeting the eligibility criteria, and who are considered protocol violators as well as patients excluded from efficacy analysis, will be identified and described by individual data listings.

Protocol deviations that will exclude patients from analysis populations are defined in section [7](#).

9.3. Demographics and Other Baseline Characteristics

Demographic information, disease history, medical history, prior antitumor therapies/ procedures for enrolled patients, will be provided as listings.

Descriptive statistics for demographic data will be generated for both enrolled and treated patients by study phase. Other baseline characteristics such as history of current and other tumors, relevant medical history, previous antitumor treatments and procedures, and vital signs will be generated across all treated patients by study phase.

The baseline assessment corresponds to the last non-missing analysis performed before initial study drug administration, unless otherwise indicated in the appendix TLGs Mock-ups and Algorithms.

Frequency distributions will be presented for the categorical/categorized variables (e.g. sex, ECOG PS and race). Summary statistics including mean, standard deviation, median, minimum, maximum and the number of assessed patients will be calculated, as appropriate, for the quantitative variables (e.g. age, weight, systolic and diastolic blood pressure).

The continuous data, such as age, will also be described in classes.

9.4. Previous or Concomitant Medications/ Procedures

Previous or concomitant medications/procedures will be descriptively analyzed in the treated patient population by dose level and by Study Phase, and reported in data listings. Previous or concomitant medications will be coded by World Health Organization Drug (WHODrug) Global B3 dictionary [\[11\]](#). The frequency and percentage of all previous or concomitant medications will be summarized by preferred term. Patients will only be counted once within preferred term. Previous or concomitant procedures/radiotherapy will be coded by Medical Dictionary for Regulatory Activities (MedDRA) and the number and percentage of subjects with previous or concomitant procedures/radiotherapy will be summarized by MedDRA preferred term [\[12\]](#).

9.5. New Anticancer Therapies / Procedures

Statistical Analysis Plan

No other approved or investigational anticancer treatment will be permitted during the study treatment period, including chemotherapy, immunotherapy, biological response modifiers, and hormones.

New antitumor systemic therapies, new radiotherapies and new procedures after discontinuation of study treatment will be provided respectively in a data listing.

9.6. Treatment Exposure and Compliance

For each study phase, the treatment exposure and the compliance with study treatment will be descriptively analyzed in the treated patient population. Descriptive statistics (e.g. min, max, mean, standard deviation, and median value) will be calculated on a per-patient basis for the following variables: the number of cycles administered, the overall duration of treatment, the actual and total doses administered, and the absolute and relative dose intensity. Frequency distributions of patients and/or cycles will be used to describe dose modifications such as dose delayed, dose increased, dose omitted, infusion slowed, infusion interrupted and cycle delayed or in advance, as well as the reasons for deviation from the planned therapy. Individual data will be presented in listings as reported in the relevant CRF sections.

9.7. Efficacy Analyses

The efficacy of NMS-01940153E will be assessed on the treated set for Phase I and evaluable set for Phase II, respectively, as defined in Section 7. For Phase II, only if deemed of interest and only as supportive analysis, efficacy could be also evaluated on the treated population.

Event dates, censoring definitions for time-to-event efficacy endpoints and other specific definitions are provided in the separate appendix TLGs Mock-ups and Algorithms.

9.7.1. Primary Efficacy Endpoint(s)

For Phase II part, the primary efficacy endpoint ORR will be evaluated as the proportion of patients who have achieved as best overall response, CR or PR as defined by investigator assessed RECIST 1.1. In addition to the point estimate, binomial exact 95% confidence intervals will be provided.

The decision rules for interim analysis for futility are specified in Section 5.2.

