For the Phase II, the investigator-assessed objective response rate will be the primary outcome measure. The sample size is based on precision considerations for the estimate of the primary efficacy endpoint. A single-group design will be used to obtain a one-sided 95% lower-limit confidence interval for a single proportion. The sample proportion is assumed to be 0.3. To produce a confidence interval with a distance from the sample proportion to the lower limit of no more than 0.12, 38 patients will be needed.

A lower bound of 18% for ORR by RECIST 1.1 would be meaningful relative to second line therapies in HCC. The emergence of atezolizumab with bevacizumab in first line has obscured true current second line outcomes with regorafenib, lenvatinib or sorafenib but it is logical to assume second line ORR would be no better relative to the pre-atezolizumab/bevacizumab era in which sorafenib was the first line standard. Prior to the atezolizumab/bevacizumab era, regorafenib in second line showed ORR of 11% by mRECIST and cabozantinib of 4%, nivolumab 15%, pembrolizumab 18% and apatinib 10.7% assessed by RECIST 1.1. Therefore, in the third line setting following failure of atezolizumab/bevacizumab in first line followed by TKI in second line, and where current third line standards are not yet defined, it is reasonable to expect historical ORR no higher than 18%. Accounting for a 10% proportion of non-evaluable patients, up to 43 patients could be required for completing the trial, however, the Phase II part of the study will not enroll beyond 40 subjects unless discussed and agreed with FDA or relevant health authority based on emerging response rates.

Interim Analyses:

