12. STATISTICAL METHODS

12.1. Sample Size Calculation

An overall sample size of approximately 55 patients may be anticipated considering both phases of the study.

For the Phase I, approximately 12-15 treated patients may be expected. Since the trial design foresees that sequential dose-escalation steps are applied to cohorts of 3 to 6 patients up to the identification of the MTD, the number of patients who will be enrolled and treated may vary, depending upon the toxicity observed that will influence cohort size and number of dose levels tested.

For the Phase II, the investigator-assessed objective response rate by RECIST 1.1. will be the primary outcome measure.

The sample size is based on precision considerations for the estimate of the primary efficacy endpoint. A single-group design will be used to obtain a one-sided 95% lower-limit confidence interval for a single proportion. The sample proportion is assumed to be 0.3. To produce a confidence interval with a distance from the sample proportion to the lower limit of no more than 0.12, 38 patients will be needed. A lower bound of 18% for ORR by RECIST would be meaningful relative to second line therapies in HCC. The emergence of atezolizumab with bevacizumab in first line has obscured true current second line outcomes with regorafenib, lenvatinib or sorafenib but it is logical to assume second line ORR would be no better relative to the pre-atezolizumab/bevacizumab era in which sorafenib was the first line standard. Prior to the atezolizumab/bevacizumab era, regorafenib in second line showed ORR of 11% by RECIST1.1 [10] and cabozantinib 4% [22], nivolumab 15% [23], pembrolizumab 18% [24] and apatinib 10.7% [25]. Therefore, in the third line setting following failure of atezolizumab/bevacizumab in first line followed by TKI in second line, and where current third line standards are not yet defined, it is reasonable to expect historical ORR no higher than 18%. Accounting for a 10% proportion of non-evaluable patients and if the stopping rule for futility is not met, up to 43 patients could be required for completing the trial, as reported in detail in Section 12.4; however, the Phase II part of the study will not enroll beyond 40 subjects unless discussed and agreed with FDA or relevant health authority, based on emerging response rates.

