12.3.4.1. Primary Efficacy Endpoint

For Phase II part, the primary efficacy endpoint ORR will be evaluated as the proportion of patients who have achieved as best overall response, CR or PR as defined by investigator-assessed RECIST 1.1. In addition to the point estimate, binomial exact confidence intervals will be provided.

The decision rules for interim analysis for futility are specified in Section [12.1](#).

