4.3. Sample Size

An overall sample size of approximately 55 patients may be anticipated considering both phases of the study.

For the Phase I, approximately 12-15 treated patients may be expected. Since the trial design foresees that sequential dose-escalation steps are applied to cohorts of 3 to 6 patients up to the identification of the MTD, the number of patients who will be enrolled and treated may vary, depending upon the toxicity observed that will influence cohort size and number of dose levels tested.

For the Phase II, the investigator-assessed objective response rate by RECIST 1.1. [2] will be the primary outcome measure. The sample size is based on precision considerations for the estimate of the primary efficacy endpoint. A single-group design will be used to obtain a one-sided 95% lower-limit confidence interval for a single proportion. The sample proportion is assumed to be 0.3. To produce a confidence interval with a distance from the sample proportion to the lower limit of no more than 0.12, 38 patients will be needed. A lower bound of 18% for ORR by RECIST would be meaningful relative to second line therapies in HCC. The emergence of atezolizumab with bevacizumab in first line has obscured true current second line outcomes with regorafenib, lenvatinib or sorafenib but it is logical to assume second line ORR would be no better relative to the pre-atezolizumab/bevacizumab era in which sorafenib was the first line standard. Prior to the atezolizumab/bevacizumab era, regorafenib in second line showed ORR of 11% by RECIST1.1 [3] and cabozantinib 4% [4], nivolumab 15% [5], pembrolizumab 18% [6] and apatinib 10.7% [7]. Therefore, in the third line setting following failure of atezolizumab/bevacizumab in first line followed by TKI in second line, and where current third line standards are not yet defined, it is reasonable to expect historical ORR no higher than 18%. Accounting for a 10% proportion of non-evaluable patients and if the stopping rule for futility is not met, up to 43 patients could be required for completing the trial, as reported in detail in Section 5.2; however, the Phase II part of the study will not enroll beyond 40 subjects unless discussed and agreed with FDA or relevant health authority, based on emerging response rates.

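### Phase II is sized on a one-sided 95% lower limit for ORR, but the analysis text gives only a 95% interval with no side; read as two-sided, the precision at 38 patients is about 0.14, not 0.12

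*SAP*

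**What the plan says.** The sizing text is essentially the same in Protocol 12.1, the Protocol synopsis (1.4) and SAP 4.3. The SAP sets the basis: "A single-group design will be used to obtain a one-sided 95% lower-limit confidence interval for a single proportion". It continues: "The sample proportion is assumed to be 0.3". Protocol 12.1 gives the precision and the number as a "distance from the sample proportion to the lower limit of no more than 0.12, 38 patients will be needed". The benchmark follows in the synopsis, "A lower bound of 18% for ORR by RECIST 1.1 would be meaningful relative to second line therapies in HCC", and in almost the same words in Protocol 12.1 and SAP 4.3.

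The analysis text is thinner:

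- SAP 9.7.1 (primary endpoint): "In addition to the point estimate, binomial exact 95% confidence intervals will be provided".
- SAP 8 (general specifications): the ORR "will be reported both as a point estimate and by means of 95% CIs".
- Protocol 12.3.4.1: "In addition to the point estimate, binomial exact confidence intervals will be provided", with neither level nor side.

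None of these three sections mentions the one-sided limit or the 18% bound.

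**The concern.** Precision is the only stated basis for the 38 patients, so the interval that is reported should be the one whose precision was planned. A 95% interval with no side given is ordinarily taken as two-sided. SAP 9.7.2 uses the same expression for the mRECIST ORR and for the Kaplan-Meier estimates, where two-sided is the natural reading, and nothing marks the primary ORR interval as different. The lower end of a two-sided 95% interval is a one-sided 97.5% limit, which lies further from the estimate than the limit used for sizing.

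What is at stake is stated precision and interpretation. A reader who sets the reported lower limit against 18% would be using a different limit from the one that produced both the 18% (0.30 − 0.12) and the 38. The trial is open-label with a single arm, so leaving the choice of limit open until the responses are known invites a doubt that can be removed now.

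**Working it through.** **Inputs.** Assumed ORR p = 0.30, maximum distance 0.12, one-sided 95% level and n = 38 (Protocol 12.1, synopsis, SAP 4.3). Exact binomial intervals (Protocol 12.3.4.1, SAP 9.7.1) and a 95% level with no side (SAP 8, SAP 9.7.1). The sizing text does not name its method.

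**Formula.** The exact (Clopper-Pearson) lower limit for x responders in n is the a-quantile of a Beta(x, n − x + 1) distribution. Use a = 0.05 for a one-sided 95% limit and a = 0.025 for the lower end of a two-sided 95% interval. The distance is x/n minus this limit. For sizing, x = 0.30n is left unrounded.

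**Step 1: reproduce the plan's 38** (a = 0.05).

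- n = 37: distance 0.1212, too wide.
- n = 38: x = 11.4, lower limit 0.1803, distance 0.1197.

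The smallest n meeting 0.12 is 38, as stated. The smallest n under other one-sided 95% methods is:

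| Method | Smallest n |
|---|---|
| Exact (Clopper-Pearson) | 38 |
| Wald | 40 |
| Wald, continuity-corrected | 48 |
| Wilson | 28 |
| Wilson, continuity-corrected | 36 |
| Agresti-Coull | 29 |
| Jeffreys | 31 |

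Of these, only the exact method gives 38, so it is inferred to be the sizing method. The inflation also reproduces: 38/0.9 = 42.2, rounded up to 43.

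**Step 2: two-sided 95% exact interval at the same n and p** (a = 0.025). At n = 38 the lower limit is 0.1625 and the distance 0.1375. Holding 0.12 on this basis would take 52 evaluable patients.

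**Step 3: achievable counts.** Since 11.4 responders cannot occur, the whole-number results at n = 38 are:

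| Responders | ORR | One-sided 95% lower limit (distance) | Two-sided 95% lower limit (distance) |
|---|---|---|---|
| 11 | 28.9% | 17.2% (0.118) | 15.4% (0.135) |
| 12 | 31.6% | 19.3% (0.122) | 17.5% (0.141) |
| 13 | 34.2% | 21.6% (0.126) | 19.6% (0.146) |

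Exceeding 18% takes 12 of 38 on the sizing basis and 13 of 38 on the two-sided basis. If 40 patients were analysed, 12 of 40 is exactly 30%, and the limits are 18.3% and 16.6%.

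**The case against.** The strongest reply is that the documents are silent on sidedness, not contradictory. SAP 4.3 says which limit the design is meant to obtain, and 9.7.1 can be read in that light. SAP 8.2 also sends analysis conventions to a separate appendix of mock-ups and algorithms, which was not available to us and may state the side. This stands as a limit on the finding: the two-sided reading is inferred. It does not remove the need to state the side of the primary interval where that interval is defined.

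It can also be said that nothing turns on it. Phase II has no success rule and the 18% is a yardstick. The only efficacy decision is the futility rule at 10 evaluable patients, which uses no interval. A two-sided interval would understate, not overstate, the drug against 18%. The shift is one responder, and 0.12 is nominal even on the sizing basis, since 12 of 38 gives 0.122. All of this is correct. It bounds the consequence, but the precision that justified 38 would still differ from that of the interval apparently to be reported.

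Finally, the Protocol leaves detail to the SAP, so the missing level in Protocol 12.3.4.1 is filled by the SAP's 95%. That is fair for the level. The side is missing from both documents.

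**Conclusion.** The concern holds. The sample size is right on its own terms: 38 reproduces exactly as a one-sided 95% exact calculation. The analysis text does not carry that limit forward. Read conventionally, it delivers a distance of about 0.14 and a lower limit of about 16% at the assumed ORR, in place of 0.12 and 18%. The difference is 0.1375 − 0.1197 = 0.018, or one responder when set against 18%.

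This rests on two inferences: that an unlabelled 95% interval is two-sided, and that the sizing used the exact method. The arithmetic, and the absence of a stated side in the supplied text, are certain. What the unseen appendix says is not. The point should be fixed, but it affects stated precision and interpretation only. No trial decision changes and no data are lost.

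**What to change.** Choose one of two routes.

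1. **Carry the sizing limit forward.** In SAP 8, SAP 9.7.1 and Protocol 12.3.4.1, state that the primary ORR will be reported with its exact (Clopper-Pearson) one-sided 95% lower limit, which equals the lower end of the exact two-sided 90% interval. Say that this limit matches the sample-size basis and is the one read against 18%. Show the two-sided 95% interval as well.
2. **Keep a single two-sided 95% interval.** Label it two-sided in those sections, and restate the precision in Protocol 12.1, the synopsis and SAP 4.3 as about 0.14 (lower limit about 16%) at 38 patients.

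Either way, name the exact method in the sizing text and make the mock-ups appendix agree.

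The cost is a sentence in each section named. The number of patients, the futility rule and trial conduct are unchanged. The drawback is a second interval in the report under the first route, or a less favourable stated precision under the second.

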9.7.2. Secondary Efficacy Endpoint(s)

For the Phase I part, the objective tumor response (Partial and Complete response) will be reported in patients' data listings.

Statistical Analysis Plan

ORR will be also calculated for Phase II part only, as the percentage of evaluable patients with best response equal to complete response (CR) or partial response (PR) as defined by investigator-assessed mRECIST. Binomial exact 95% confidence intervals will be also provided.

Time-to-event endpoints (i.e. DoR, PFS and OS): they will be carried out on treated set for Phase I and evaluable set for Phase II, respectively. The individual calculated times will be presented in patients' data listings together with the identification of censored vs. failure status. Time-to-event endpoints will be also summarized using Kaplan Meier (KM) curves and further characterized in terms of median, 6-month, 9-month and 12-month estimates with the corresponding 95% confidence intervals, for Phase II part only.

Reverse Kaplan-Meier method [9] will be used to estimate length of follow-up for DoR, PFS and OS by reversing censored and event observations, if applicable.

9.8. Safety Analyses

Unless otherwise indicated, all safety analyses will be performed on the treated patient population by study phase and dose level. All collected safety data (adverse events, laboratory assessments, vital signs, ECG parameters, concomitant medications etc.), will be presented in individual patients' data listings.

